8.5.3 SAFETY ANALYSES

All AEs will be summarized among the safety population by frequency. These frequencies will be presented overall and separately by dose, and will depict overall, by SOC and by preferred term, the percentage of subjects affected. Additional frequencies will be presented with respect to maximum severity and to strongest relationship to Study Treatment. Multiple occurrences of the same AE will be counted only once following a worst-case approach with respect to severity and relationship to Study Treatment. All serious AEs will also be summarized as above.

The main summary of AE data will be based on events occurring within 28 days following any dose. For this summary, the frequency of preferred term events will be summarized with percentages and 95% Clopper-Pearson confidence intervals. Separate summaries will be based on events occurring within 7 days following any dose and regardless of when they occurred.

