7.2 ADVERSE EVENTS (AEs)

An AE is defined as any unfavorable and unintended change in the structure, function, or chemistry of the body, or worsening of a pre-existing condition, temporally associated with the use of a product whether or not considered related to the use of the product. In

this study, such changes will be monitored, classified, and summarized, as Clinical or Laboratory AEs. Medical condition/diseases present before starting the investigational drug will be considered AEs only if they worsen after starting study treatment. Throughout the course of the study, all solicited and unsolicited AEs will be monitored and reported on an AE eCRF, including the event's seriousness, severity, action taken, and relationship to IP. Adverse Events should be followed until resolution or stable and the outcome will be documented on the appropriate eCRF. All AEs should be recorded in standard medical terminology rather than the subject's own words.

Adverse Events include the following:

- Pre- or post-treatment complications that occur as a result of protocol mandated procedure during or after Screening (before the administration of study drug);
- Any pre-existing condition that increased in severity, or changes in nature during or as a consequence of the study drug phase of a human clinical trial, will also be considered an AE;
- Complications of pregnancy (e.g. spontaneous abortion, miscarriage, ectopic pregnancy, fetal demise, still birth, congenital anomaly of fetus/newborn);
- AEs that occur from the study Screening visit onwards and throughout the duration of the study, including the follow-up off study drug period will be recorded as an AE;
- Conditions that lead to a medical or surgical procedure.

Adverse Events do not include the following:

- Medical or surgical procedures (e.g. surgery, endoscopy, tooth extraction, transfusion) performed as a result of an AE;
- Pre-existing diseases or conditions or laboratory abnormalities present or detected before the Screening visit that do not worsen;
- Situations where an untoward medical occurrence has not occurred (e.g. hospitalization for elective surgery, social and/or convenience admissions);
- Overdose without clinical sequelae;
- Any medical condition or clinically significant laboratory abnormality with an onset date before the ICF is signed is not an AE. It is considered to be pre-existing and will be documented on the medical history eCRF;
- Uncomplicated pregnancy;

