7.6 ASSESSING SEVERITY (INTENSITY)

Adverse events should be captured once on the eCRF at the maximum severity reported.

The Investigator will grade laboratory AEs and clinical AEs or SAEs with respect to the following levels of severity as per CTCAE v 4.03 for applicable patient populations:

- Mild (Grade 1)
- Moderate (Grade 2)
- Severe (Grade 3)
- Potentially Life Threatening (Grade 4)

The Investigator will grade injection site reactions in accordance with September 2007 FDA Guidance for Industry – Toxicity Grading Scale for Healthy Adult and Adolescent Volunteers Enrolled in Preventive Vaccine Clinical Trials.

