7.11 METHODS AND TIMING OF COLLECTION OF SAFETY DATA

Non-serious AEs and SAEs (and UADEs) will be collected for each subject from the time when informed consent is obtained through Week 88.

The sources of AEs cover:

1. The subject's response to questions about his/her health (a standard non-leading question such as 'How have you been feeling since your last visit?' is asked at each visit).
2. Symptoms spontaneously reported by the subject.
3. Evaluations and examinations where the findings are assessed by the Investigator to be clinically significant changes or abnormalities.
4. Other information relating to the subject's health becoming known to the Investigator (e.g. hospitalization).

All AEs will be reported on the appropriate eCRF.

Any SAE occurring during the course of the study must be reported to the Sponsor within 24 hours of awareness.

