8.5.8 MISSING VALUES

For AE data, partial start dates will be imputed to the date of treatment to conservatively report the event as treatment-emergent whenever the portion of the date is consistent with that of the study treatment. Otherwise, it will be imputed to the earliest date consistent with the partial date. A completely missing onset date will be imputed as the day of treatment. Partial stop dates will be assumed to be the latest possible day consistent with the partial date.

No other missing data will be imputed or replaced.

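### Section 7.6 records each adverse event once at its highest grade with no date of worsening, so the windowed and by-dose summaries in 8.5.3 cannot place a worsening that follows a later dose (minor)

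*Protocol*

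**What the plan says.** All references are to protocol version 3.0; the earlier version bound with it uses the same words on these points.

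- **Recording (7.6).** "Adverse events should be captured once on the eCRF at the maximum severity reported". Each event therefore has one record and one grade. No section asks for a dated grade change or a fresh entry when an event already on the eCRF gets worse.
- **Analysis (8.5.3).** "The main summary of AE data will be based on events occurring within 28 days following any dose". In addition, "Separate summaries will be based on events occurring within 7 days following any dose and regardless of when they occurred". On doses: "These frequencies will be presented overall and separately by dose". On grade: "Additional frequencies will be presented with respect to maximum severity and to strongest relationship to Study Treatment". Repeat occurrences of the same event are collapsed to one per subject, taking the worst grade and strongest relationship.
- **Dates (8.5.8).** Where a date is incomplete, "partial start dates will be imputed to the date of treatment to conservatively report the event as treatment-emergent". This is the only date rule for adverse events, and it works on the start date.
- **Definition (7.2).** Adverse events include "Any pre-existing condition that increased in severity, or changes in nature during or as a consequence of the study drug phase". Conditions present before study drug count as adverse events only if they worsen after treatment starts.
- **Collection (7.11).** Adverse events "will be collected for each subject from the time when informed consent is obtained through Week 88".
- **Status of Section 8.** Section 8.1 describes what follows as the formal statistical analysis plan.

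**The concern.** Three of the planned outputs (28-day, 7-day and by-dose) need to know when an event, and ideally its grade, fell relative to a dose. The recording rule keeps one grade and no date for reaching it. An event that starts mildly between doses and becomes severe just after the next dose is the kind of event a post-dose summary should show. Its record cannot show when it became severe.

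The loss happens at data capture. If the eCRF holds only a start date and a maximum grade, no later analysis plan can recover the date of worsening from that record. What is at stake is how well the designated main safety table, and the by-dose frequencies, describe worsening after a later dose. The primary efficacy test is not touched.

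**Working it through.** The plan gives no figure to reproduce here. The check sets the rules side by side and then lays the windows over the dosing schedule.

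**Inputs.** Dose days on the nominal schedule (synopsis): Day 0, Week 4 = Day 28, Week 12 = Day 84, optional Week 40 = Day 280. Window: 28 days after each dose (8.5.3). Recording: one entry at maximum grade (7.6).

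**Windows.** Dose 1: Days 0–28. Dose 2: Days 28–56. Dose 3: Days 84–112. Dose 4, if given: Days 280–308. Doses 1 and 2 together cover Days 0–56 without a gap, which is 57 days. Dose 3 covers 29 days.

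**Days from Day 0 on which an onset falls outside every window:**

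- Before dose 3 (Days 0–83, 84 days): 84 − 57 = 27 (Days 57–83); 27/84 = 32%.
- Before dose 4 (Days 0–279, 280 days): 280 − (57 + 29) = 194 (Days 57–83 and 113–279, or 27 + 167); 194/280 = 69%.
- Before dose 2: none on nominal dates, so absence from the 28-day summary is not an issue there. By-dose placement still is.

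**Illustrative events (assumed days), one record each at peak grade:**

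| Onset | Worsens | Placed by onset | Placed if ongoing in the window |
|---|---|---|---|
| Day 65 | Day 87, 3 days after dose 3 | In no window; absent from the 28-day summary | Present; date of peak grade unknown |
| Day 150 | Day 285, 5 days after dose 4 | In no window; absent from the 28-day summary | Present; date of peak grade unknown |
| Day 10 | Day 31, 3 days after dose 2 | Present, under dose 1 only | Present under doses 1 and 2; peak grade cannot be tied to either |

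**Reading the two columns.** Section 8.5.3 speaks of events *occurring* in the window and does not define the word. Section 8.5.8 points towards onset. Under onset, the first two events drop out of the main summary and the third is linked only to dose 1. Under the ongoing reading all three are counted, but nothing on the record says which dose the peak grade followed. So neither reading lets the windowed and by-dose summaries show the worsening correctly.

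**The case against.** The strongest reply is that the protocol never says events are placed by onset. Section 8.5.8 is a missing-data rule and 8.5.3 does not cite it. That stands, so the absence from the main table is conditional. It does not remove the problem, because the ongoing reading leaves the peak grade undated.

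Four further points on the other side hold and limit the concern.

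- **A safety net exists.** 8.5.3 also calls for a summary whatever the timing, where every event appears at its peak grade. Stopping rules (3.8) and reporting of serious events and events of special interest (7.12.1, 7.15) do not run through the 28-day table. A reader might infer that severe events are lost from the report; they are not.
- **No severity-by-dose table is specified.** 8.5.3 lists frequencies by dose and, separately, frequencies by maximum severity. A reader might conclude that the plan will print the wrong grade against the wrong dose, but the text does not state such a cross-table.
- **Section 7.2 covers pre-treatment conditions.** For these, the worsening is itself the adverse event and falls after the dose. A reader might add the 70 Screening days and arrive at 97 of 154 days (63%) before dose 3 and 264 of 350 (75%) before dose 4. Those days do not belong in the count.
- **Expected toxicity is short.** Section 1.3 describes injection-site reactions as generally mild and limited to a few days, and diary events are collected for 7 days after each dose. Such events will seldom run from one dose to the next.

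Leaving the matter to a separate analysis plan is only a partial answer: 8.1 calls Section 8 the formal plan, and no plan can restore a date that the record does not hold.

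**Conclusion.** The point holds in a narrow form. The one-record rule in 7.6 cannot support the windowed and by-dose summaries in 8.5.3 for an event that begins after Day 0, persists to a later dose and worsens after it. Depending on how 8.5.3 is read, such an event is either absent from the main 28-day summary or present with a peak grade that cannot be linked to a dose.

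The exposure is 32% of calendar days before dose 3 and 69% before the optional dose 4, on nominal visit dates from Day 0. These are shares of days on which an onset would fall outside a window, not probabilities of a miscounted event. The event must also last until the dose and then get worse. The protocol gives no rate for that, and the number is probably small. It would be too strong to say that the main table is shown to understate post-dose worsening.

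Severity: minor. No efficacy conclusion depends on it.

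**What to change.** - **Section 7.6:** require a new adverse-event entry, or a dated grade change on the existing one, whenever severity increases after a study dose.
- **Section 8.5.3:** state that an event enters the 28-day, 7-day and by-dose summaries when its onset or a worsening falls in the window, at the grade reached in that window. Keep the existing rule that counts each subject once per event at the worst grade, so that extra entries do not inflate subject percentages within a summary.

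The cost is one eCRF completion instruction, one sentence of analysis text, slightly more data entry and slightly higher windowed counts.

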8.5.4 DISPOSITION

Disposition will be summarized for all randomized subjects and will include the number and percentage randomized, the number and percentage who received each dose and the number who completed the trial. The number and percentage of subjects who discontinued will be summarized overall and by reason. The number in each analysis population will also be presented.

8.5.5 DEMOGRAPHIC AND OTHER BASELINE CHARACTERISTICS

Demographic data will be summarized with descriptive statistics: mean standard deviation, minimum, median, and maximum values for continuous variables, and percentages for categorical variables for the mITT population.

The percentage of subjects with abnormal medical history findings will be summarized by body system for the mITT population.

Prior medications are those that were used and stopped before the start of the trial (prior to Day 0). Partial stop dates of prior medications will be assumed to be the latest possible date consistent with the partial date. Data for all prior medications will be summarized with percentages for the mITT population.

8.5.6 INTERIM ANALYSES

No formal interim analyses will be performed for this study. For reasons of futility (early evidence of poor efficacy of VGX-3100) or safety issues, the DSMB could recommend stopping enrollment at any time. The type I error will not be adjusted for possible early stopping due to futility.

8.5.7 MULTIPLICITY

Not applicable; there is one hypothesis that will be tested.

8.5.8 MISSING VALUES

For AE data, partial start dates will be imputed to the date of treatment to conservatively report the event as treatment-emergent whenever the portion of the date is consistent with that of the study treatment. Otherwise, it will be imputed to the earliest date consistent with the partial date. A completely missing onset date will be imputed as the day of treatment. Partial stop dates will be assumed to be the latest possible day consistent with the partial date.

No other missing data will be imputed or replaced.

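### The adverse-event onset imputation in Section 8.5.8 has no check against the stop date, so an event known to have ended before the first dose can be counted as post-dose

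*Protocol*

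**What the plan says.** Section 8.5.8 of the protocol (version 3.0) has three date rules for adverse events.

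- **Completely missing onset:** "A completely missing onset date will be imputed as the day of treatment". No condition is attached.
- **Partial onset:** "partial start dates will be imputed to the date of treatment to conservatively report the event as treatment-emergent", provided the known part of the date fits a study treatment. If it does not fit, the earliest date compatible with the known part is used.
- **Partial stop date:** "Partial stop dates will be assumed to be the latest possible day consistent with the partial date".

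The section closes with "No other missing data will be imputed or replaced".

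Section 7.11 sets the collection period: "Non-serious AEs and SAEs (and UADEs) will be collected for each subject from the time when informed consent is obtained through Week 88". Section 7.2 lists among adverse events "AEs that occur from the study Screening visit onwards and throughout the duration of the study", and separately lists complications of protocol-mandated procedures that arise before study drug is given.

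Section 8.5.3 bases the main safety table on "events occurring within 28 days following any dose", with Clopper-Pearson intervals for each preferred term. It also asks for frequencies by dose, a 7-day summary, and a summary irrespective of timing. Section 8.1 presents Section 8 as the trial's formal statistical analysis plan.

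**The concern.** The purpose of the rule is sound: when it is unknown whether an event began before or after treatment, count it as treatment-emergent. That reasoning fails once the stop date shows that the event was over before the first dose. Its onset may be unknown, but its position relative to treatment is not.

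The rule as written does not make this distinction. It would produce a record whose onset follows its end and would place a Screening event, such as a resolved biopsy complication, in the post-dose table. What is at stake is the accuracy of single-subject counts in a small safety table, and a derived dataset containing negative durations.

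**Working it through.** The plan states no figure on this point, so there is none to reproduce. The check applies the written rule to assumed records.

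**Inputs**
- Treatment days: Day 0, Week 4 (Day 28), Week 12 (Day 84), and Week 40 (Day 280) for those given a fourth dose (synopsis).
- Screening: up to 10 weeks before dosing, ending on Day -1 (Table 8).
- Main window: 28 days after any dose (Section 8.5.3).
- Denominator: 24 (Section 8.6; the synopsis says approximately 24).

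**Case 1: onset completely missing (assumed record).** A Screening event has no onset date and a recorded stop on Day -20. Gap = imputed onset minus stop date.

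| Treatment day used | Gap | Within 28 days of a dose? |
|---|---|---|
| Day 0 | 0 - (-20) = 20 days | Yes |
| Day 28 | 28 - (-20) = 48 days | Yes |
| Day 84 | 84 - (-20) = 104 days | Yes |
| Day 280 | 280 - (-20) = 300 days | Yes |

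Whichever treatment day is meant, the onset falls after the end and the event enters the main summary. If the onset could not be later than the stop date, it would be on or before Day -20, and the event would leave the 28-day, 7-day and by-dose tables.

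**Case 2: onset partial (assumed record).** First dose on 20 March; onset recorded only as March of that year; stop date 12 March. The known part fits the treatment date, so the onset becomes 20 March, which is 20 - 12 = 8 days after the event ended. The partial-date rule therefore shares the gap.

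**Could another rule prevent this?** The only stop-date rule completes partial stop dates; it does not limit the onset. No other imputation is allowed.

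**Could Section 7.2 keep such events out of the data?** One sentence there counts conditions present before study drug only if they later worsen. The same section expressly includes events from Screening onwards and pre-dose procedure complications, and Section 7.11 collects "from the time when informed consent is obtained through Week 88". A resolved Screening complication is therefore in the adverse-event data.

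**Size.** One event in one subject is 1/24 = 4.2%. For a term with no other case:
- without the event, 0/24 = 0%, with exact 95% upper limit 1 - 0.025^(1/24) = 14.2%;
- with the event, 1/24 = 4.2%, with exact 95% interval 0.1% to 21.1%. The lower limit is 1 - 0.975^(1/24) = 0.1%; the upper limit is the 97.5% point of a Beta(2, 23) distribution.

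Section 8.5.3 counts a repeated event once per subject, so the shift is zero if that subject already has an in-window event of the same term.

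**The case against.** The strongest reply is that the trigger is narrow.

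- In the completely missing case, an onset with not even a month or year must sit beside a stop date that falls before Day 0.
- Section 7.2 sends conditions that began before consent to medical history, so a site must already have some idea of when an event began before recording it as an adverse event.
- Subjects are asked about events at every visit, and Section 12.3 has monitors check case report forms against source.
- Section 6.2 starts the 10-week window at collection of the biopsy and accepts tissue from a previous biopsy. Complications that began before consent are not adverse events, so fewer Screening events are exposed than the 10 weeks suggests.

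All of this stands. It makes the record rare but does not supply the missing check.

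The reply also notes that nothing decisive depends on these tables. The one formal hypothesis concerns efficacy (Section 8.3). The pausing criteria in Section 3.8 turn on verified, related or graded events, not on imputed onsets. Relatedness is the investigator's judgement (Section 7.7). The summary irrespective of timing does not change, and any error runs towards over-reporting. This also stands and limits the importance of the point.

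That such detail may be left to a separate analysis plan is only a partial defence. The protocol fixes the rule itself, without condition, in the section it calls the formal plan.

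A reader might go further and treat the unnamed treatment day as an error in itself, because there are three or four such days and frequencies are shown by dose. That is mostly unstated detail. It is worth settling in the same edit, but it is not what makes the rule give a wrong result.

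**Conclusion.** The point holds as a minor drafting defect. For an event with a stop date before the first dose and an onset that is completely missing, or partial and compatible with a treatment date, the rule gives an onset after the end and counts the event as post-dose. This rests on the text of Sections 7.2, 7.11, 8.5.3 and 8.5.8; the two worked records are assumptions.

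The effect is at most about 4.2 percentage points per event on one preferred term, and only where the subject has no other in-window event of that term. The documents do not say how many such records to expect, and there may be none.

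A reader might infer that the safety profile as a whole would be distorted, or that every missing onset is handled wrongly. The documents do not support either. Assigning a genuinely unknown onset to treatment is a defensible conservative choice, the tables are descriptive and single-arm, and neither the primary analysis nor the pausing criteria are affected.

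**What to change.** Add to Section 8.5.8, for both completely missing and partial onsets:

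1. An imputed onset may not be later than the event's stop date, with a partial stop date first taken at its latest possible day.
2. An event whose stop date, so completed, precedes the first dose is classified as pre-treatment and kept out of the 28-day, 7-day and by-dose summaries.
3. State which treatment date is used when more than one is possible.

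Items 1 and 2 cost a sentence each and a simple programming check. They keep the conservative treatment of onsets that are truly unknown. Item 3 involves a choice: defaulting to the first dose is simple, but it loads the Dose 1 column with events that may have followed a later dose. If that convention is chosen, the by-dose table should carry a footnote giving the number of imputed onsets.
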